## Implementation framework: EPIS model.

The implementation approach is anchored in four stages of the EPIS conceptual model: Exploration, adoption/Preparation,

Implementation, and Sustainment. The strong evidence for SEEK's effectiveness has been underscored by its listing on the websites of the CDC, AHRQ, AAP, and by the California Clearinghouse for Evidence-Based Interventions in Child Welfare. Early adopters are increasingly implementing SEEK in primary care settings, including in Sweden. Four of the 5 healthcare systems in this proposal have implemented SEEK in some of their practices. However, practices within these systems operate independently of one another, and there should not be contamination among them. Each practice has its own lead physician, PCPs and administrative staff and several have integrated behavioral health. Given that early adopters are estimated to be 10% of those eligible and that medical innovations can take 17 years to be adopted, it is unlikely that SEEK's potential public health benefit will be realized without better methods for scaling up.

**Design.** The proposed implementation study is the first involving SEEK. We selected a rigorous Hybrid Type III design which is an approach to examine implementation outcomes while also examining SEEK's effectiveness in preventing CM, measured by EHR indicators. Type III designs are facilitated by good EHR systems due to the low cost of data routinely gathered for clinical, services, and financial purposes. This allows more resources to address the implementation outcomes of SEEK strategies in routine practice settings. In the past 4 years, over 80 papers reported use of hybrid designs. Practices will be randomized to one of the two training strategies (IND vs. MOC). Practices, however, will be able to select the facilitation strategy (SEEKonline or Traditional) as we are not able to require this of participants. The design accounts for heterogeneity in geography, size of healthcare systems, type of primary care (pediatric and family medicine), and presence of integrated behavioral health (see strong support letters from healthcare systems in Texas, Ohio, Utah, Wisconsin and North Carolina). As shown in Figure 2, professionals, office staff and parents are

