**Recruitment.** Leaders in the 5 healthcare systems will be approached to formally approve participation, without committing individual practices. A letter will be sent to physician leaders of practices inviting participation in the study. If interested, we will hold a 1-hour webinar with the practice leader, PCPs and behavioral health professionals together with key office staff. We will provide written material detailing what their involvement will entail. Participation will be voluntary, and, while we prefer that all the PCPs in a practice participate, this will not be required. We anticipate that behavioral health professionals and office staff will necessarily be involved in practices opting to participate. We will sign an MOU with participating practices, and request a limited informed consent by practice leaders and PCPs who opt out, to gather data regarding their decision and practice demographics. Informed consent will be obtained from all participants. This will be done online at the beginning of the first survey, an approach we used successfully in SEEK II. We will recruit one practice manager and nurse per practice. Finally, parents will be recruited via flyers describing the project in the waiting area. If interested, they will be asked to notify staff who will request their contact information and permission to convey their interest to SEEK project staff. We will contact them and explain the project by phone and in writing. Prior to the start of the first online survey, participant consent will be obtained.

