### **Procedures**

**Pre-implementation Phase** (5 months). Recruitment will begin and we will identify a physician "champion" and an office staff member to lead implementation in each practice. Practices will choose by month 4 SEEKonline or the Traditional paper and pencil approach. To ease introduction of the SEEK model, we will address logistical issues such as for which checkups parents will complete the SEEK PQ and documentation in the EHR. SEEK Parent Handouts will be customized with information on local resources and PCPs will complete the SEEK Primary Care Provider Questionnaire (PCPQ) prior to the SEEK training.

**Implementation Phase.** In month 5, practices in cohort 1 will be randomized to one of the two SEEK training strategies (MOC or IND), stratified by practice type (pediatric or family medicine). At the end of training in month 8, PCPs will evaluate it. After the training, PCPs will be asked to participate in 3 webinars

every 4 months to discuss implementation and clinical issues. By month 8, interested practices will have SEEKonline connected to their EHR, ensuring interoperability. In month 9, the SEEK intervention will begin in cohort 1. Practice leaders, PCPs, behavioral health professionals and office staff will be asked to complete the online SEEK Adoption Survey, regardless of full participation. Parents also will begin completing surveys. Purposive subsamples from each group will be selected for 30-minute phone qualitative interviews. The process for cohort 2 will begin in month 11 and the SEEK intervention will start in month 16. Procedures are detailed under Human Subjects for addressing concerns of possible child abuse or neglect.

**Sustainment Phase.** Participants will be assessed at 12, 21 and 33 months post baseline regarding their thinking, feeling, behavior and experiences (see Table 3) to help inform understanding of SEEK's implementation and sustainment. At months 41 and 48, the observation period will end for cohorts 1 and 2. Final surveys and phone interviews will assess participants' thoughts and plans about continued use of SEEK. Following the grant period, practices that wish to continue utilizing the implementation strategies will be guided through the process of establishing real-world, not-grant funded contracting.

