**Table 3: Study Measures Related to Specific Aims**

Domain/Measure	Aims	Respondent*	Baseline** A: mo 8 B: mo 15	Training A: by mo 9 B: by mo 10	F/U 1 A: mo 20 B: mo 27	F/U 2 A: mo 29 B: mo 30	F/U 3 A: mo 41 B: mo 48
Organizational							
System Demographics	1, 2, 3	SL	●			●	
Evidence Based Practice Attitude Scale	1, 2, 3	All, except parents	●		●	●	●
Implementation Leadership Scale	1, 2, 3	All, except parents	●		●	●	●
Implementation Climate	1, 2, 3	All, except parents	●		●	●	
Implementation Process							
Stages of Implementation	2, 3	AS	●	●	●	●	●
Adoption							
SEEK Adoption Survey	2, 3	SL, PL, PCP	●				
Seek Training							
SEEK Training Evaluation	1, 2, 3	PCP		●			
Child Maltreatment							
EHR review****		IT			●		●
Implementation Outcomes							
SEEK PCP Questionnaire	1, 2, 3	PCP	●	●	●	●	●
SEEK PCP Survey	1, 2, 3	PCP		●	●	●	●
SEEK Office Staff	1, 2, 3	AS		●	●	●	●
SEEK Parent View	1, 2, 3	P		●	●	●	●
Rate of Screening	1, 2, 3	EHR	●	●	●	●	●
Receipt of Services	1, 2, 3	EHR	●	●	●	●	●
Costs							
Cost of Implementing New Strategies (COINS)	2, 3	PL, AS, PCP			●	●	●
General							
Qualitative Phone Interviews	1, 2, 3	All		●	●	●	●

\*SL = system leaders, PL = practice leaders, PCP = primary care providers, BHP = behavioral health professionals, AS=ancillary staff, P=parents, BHP=behavioral health professional, IT=information technology

\*\*A = 1st cohort of healthcare systems and practices, B = 2nd cohort of healthcare systems and practices

\*\*\*\*Brief Child Abuse Potential Inventory, \*\*\*\*EHRs will be reviewed by IT toward end of study

Proportion Scores are calculated separately for each stage. The total Proportion Score is based on the number of activities completed out of the number that could be completed – for each stage.

Finally, the SIC Stage Score marks the final stage that a site reaches. SIC scores are calculated within each of the three Implementation Phases: Pre-implementation (stages 1-3), Implementation (stages 4-7), and Sustainment (stage 8).

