**Aim 1. Compare alternative approaches to implementation of SEEK with respect to clinical and implementation outcomes.** To address aim 1a, we will compare practices randomized to MOC to practices randomized to IND with respect to clinical and implementation outcomes. These include perceptions of the training from the PCPs' evaluations, scales from the SEEK PCPQ (e.g., Competence in addressing problems) and the PCP Survey (e.g., Ease of Delivery. We will also compare the groups with respect to rates of screening and parents' receipt of services and satisfaction with the PCP. For quantitative outcomes, statistical inference will be based on linear regression models; for binary outcomes, inference will be based on logistic regression models, accounting for repeated measures within PCP and system. For example, for PCPs reported Competence we will fit this model:  $E(\text{Competence}_{ijkl}) = \beta_0 + s_i + p_j + i_k + \beta_1(\text{POST}) + \beta_2(\text{POST})(\text{MOC-4})$  where Competenceijkl stands for the competence score measured at the lth time point (l=1 or 2 for baseline or follow-up respectively) of the kth PCP in the jth practice of the ith system, and  $s_i$ ,  $p_j$ ,  $i_k$  are random effects for system, practice and PCP respectively; POST=1 if it is a post-training measure and 0 otherwise, MOC = 1 if the PCP was trained using MOC and 0 if IND, and  $\beta$ 's are parameters to be estimated. Note this model assumes that the mean baseline scores are the same in both groups, as recommended for randomized studies. This model can be fitted using restricted maximum likelihood. To avoid possible biases due to selective attrition from the training, the primary analysis will follow the "intention to treat" principle including all those randomized. Secondary analyses will be based on groups defined by training received. To address Aim 1b we will compare practices who choose SEEK-online to practices who choose the traditional approach using the same statistical methods as described for Aim 1a. Outcomes of interest will include staff satisfaction, costs, rates of screening, receipt of services, and parental satisfaction.

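### No rule requires PCP consent and baseline before the practice's training allocation is released, and the documents conflict on the order, so PCPs can join or decline knowing their arm

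*Combined protocol and SAP*

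**What the plan says.** The practice is the unit of randomisation: "Practices will be randomized to one of the two training strategies (IND vs. MOC". For cohort 1 the month is given under Procedures, Implementation Phase: "In month 5, practices in cohort 1 will be randomized to one of the two SEEK training strategies (MOC or IND". Joining is an individual decision. The Recruitment paragraph says that "while we prefer that all the PCPs in a practice participate, this will not be required", and of informed consent for all participants: "This will be done online at the beginning of the first survey, an approach we used successfully in SEEK II".

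Three places bear on when a PCP's first survey falls:

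- **Procedures.** The PCPQ appears in the Pre-implementation Phase paragraph, before the paragraph that opens with randomisation. The only condition attached is that it precede training. Training comes after randomisation and finishes in month 8: "At the end of training in month 8, PCPs will evaluate it".
- **Timeline.** Evaluation of participants starts in month 5, the month of randomisation.
- **Table 3.** The baseline column, which includes the PCPQ, is headed "Baseline A: mo 8 B: mo 15".

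The arms ask for different work. Under Training and Table 1, both include the videos, the post-test and three consultations. MOC adds four one-hour webinars and a quality improvement project, and carries MOC-4 credit.

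For Aim 1, the Data Analysis Plan makes the primary analysis intention to treat, a "principle including all those randomized". Its model constrains the mean baseline score to be equal in the two arms, on the ground that the study is randomised.

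**The concern.** In a cluster-randomised trial, randomisation protects the comparison of individuals only if those individuals are identified before allocation is known, or are enrolled without regard to it. Here a PCP becomes a participant by consenting at a survey that no sentence places before allocation, and that Table 3 places after it. A PCP who learns which training the practice drew can decide on that basis whether to take part.

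Aim 1a (attitudes, comfort and competence) is the main randomised comparison, and those outcomes plausibly follow motivation. The stated purpose of intention to treat is to deal with selective attrition from training, which is loss after entry. A PCP who never consents supplies no PCPQ, so the principle has nothing to retain. Selective entry also removes the reason for assuming equal baseline means.

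**Working it through.** **1. Dates, cohort 1.** Randomisation is in month 5, training ends in month 8, and the Table 3 baseline is month 8. The gap from allocation to baseline is 8 − 5 = 3 months, and baseline falls in the month training ends.

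**2. Is month 8 a misprint?** Procedures states: "Participants will be assessed at 12, 21 and 33 months post baseline". Table 3 puts the cohort 1 follow-ups at months 20, 29 and 41. Then 20 − 8 = 12, 29 − 8 = 21 and 41 − 8 = 33, so month 8 is the origin of the follow-up schedule. That does not prove the PCPQ is first given in month 8. It does mean that following Table 3 as written puts baseline after allocation.

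**3. Cohort 2.** Baseline is month 15: 27 − 15 = 12 and 48 − 15 = 33 fit. The second follow-up at month 30 does not, since 15 + 21 = 36. No randomisation month is given. Cohort 1 randomises 9 − 5 = 4 months before the intervention starts. The same lead before the month 16 start would give month 12, again before baseline. That is an inference.

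**4. The plan's own detectable effect.** Table 4 gives 0.42 SD for 137 PCPs per group, 80% power and two-sided 0.05, with variance inflated 1.5-fold.

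- Normal approximation: (1.960 + 0.842) × √(1.5 × 2/137) = 0.415.
- t test on 137/1.5 = 91.3 per group: 0.417.

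The figure reproduces.

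**5. Raw bias (assumed inputs).** The documents give no decline rates by arm. If a share q declines and decliners would score g SD below joiners, the joiners' mean exceeds the mean of all PCPs by q × g. The bias is (q for MOC − q for IND) × g. With g = 0.5:

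| Decline, MOC | Decline, IND | Raw bias (SD) | Share of 0.42 |
|---|---|---|---|
| 20% | 5% | 0.100 − 0.025 = +0.075 | 18% |
| 30% | 5% | 0.150 − 0.025 = +0.125 | 30% |
| 5% | 20% | 0.025 − 0.100 = −0.075 | 18%, opposite sign |

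**6. After the planned model.** The model treats baseline as a repeated outcome with a PCP random effect, so it acts much like baseline adjustment. It removes roughly a fraction ρ of a stable imbalance, where ρ is the pre-post correlation. For the first row, with ρ assumed:

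- ρ = 0.3: 0.075 × 0.7 = 0.053 SD
- ρ = 0.5: 0.075 × 0.5 = 0.038 SD
- ρ = 0.7: 0.075 × 0.3 = 0.023 SD

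This is about 0.02 to 0.05 SD, or 5% to 13% of 0.42. It needs a baseline measured before training, and it does not cover selection on traits that baseline scores miss, such as willingness to learn.

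**7. Power.** If 10%, 20% or 30% of MOC PCPs opt out, that arm falls from 137 to about 123, 110 or 96. Power at 0.42 falls from 0.81 to 0.79, 0.76 or 0.73. The main issue is bias.

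**The case against.** The documents can be read more kindly. The PCPQ sits under the pre-implementation heading, ahead of randomisation, which suggests that a pre-allocation baseline was intended. Table 3 is an imperfect witness: a first PCPQ at the end of training would contradict Procedures, and its cohort 2 column has other misfits, including training by month 10 when that cohort's process starts in month 11. Recruitment also has earlier steps: a webinar for PCPs, written material on what involvement entails, and a signed MOU. The Timeline lists recruiting practices before assigning them, so many opt-out decisions may come before allocation. In SEEK II every PCP in a joining practice took part, with the same online consent.

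Much of this stands. A reader might infer that the sponsor chose to take consent after allocation. The documents do not show that; they show a conflict and a missing rule. But the pre-implementation phase lasts five months and so reaches the month of randomisation, and the only stated anchor for the PCPQ is training. Neither the webinar nor the MOU is said to fix who is enrolled. SEEK II compared SEEK with standard care, not two training loads, and this protocol itself plans for PCPs who opt out.

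A reader might also infer that the MOC effect will be overstated. That does not follow. MOC-4 credit is an incentive that may offset or outweigh the extra work, so differential refusal could be nil or reversed.

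**Conclusion.** The concern holds as a conflict over timing together with a missing safeguard. As written, PCPs in cohort 1 can enter or decline knowing their arm; for cohort 2 the order is inferred. Intention to treat does not cover refusal at entry, and randomisation no longer guarantees the equal-baseline assumption.

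Neither the direction nor the size of any bias is known. The illustrative 0.075 SD, and the 0.02 to 0.05 SD left after modelling, rest on assumed decline rates, an assumed 0.5 SD gap and assumed correlations. It would be too strong to say that a baseline difference passes wholly into the estimated effect, or to give 18% to 30% of the detectable effect as the expected harm, because the planned model removes part of a stable imbalance. That relief depends on a true pre-training baseline, which Table 3 puts in doubt.

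The change should be made before randomisation, because selective entry cannot be repaired afterwards.

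**What to change.** Reconcile the Timeline, Procedures and Table 3, and state one order for both cohorts:

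- PCP consent and the baseline PCPQ are completed, and the practice's PCP roster is closed, before its allocation is released. In cohort 1 this can be by month 4, when practices must already choose SEEKonline or Traditional. For cohort 2, give the randomisation month.
- The intention-to-treat set for Aim 1a is the PCPs on that roster, by the allocation of their practice.
- PCPs who join or consent later are trained but analysed only in a secondary set.
- Opt-outs are reported by arm, before and after release of allocation.

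The cost is moving one online survey ahead of randomisation and adding a sentence on the analysis set. A practice's randomisation may wait a few weeks for its roster to close.

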### **Timeline** (See Table 3 for timing of data collection)

Month 1-8: Hire and train project coordinator and research assistant. Randomly select first 2 healthcare systems (one pediatric, one family medicine). Recruit practices and randomly assign to SEEK training strategies; complete training. Practices select SEEKonline or Traditional strategy, SEEKonline connected to practices' EHRs, computerize study protocol, obtain IRB approvals

Month 5-48: Periodic webinars with PCPs and evaluation of participants, develop papers and presentations

Month 9: Begin implementing SEEK model in cohort 1 of healthcare systems and practices

Month 11-15: Repeat above process with cohort 2 of healthcare systems and practices

Month 16: Begin implementing SEEK model in cohort 2

Month 46-48: End of observation period, practices decide whether to continue using SEEK, final surveys

Month 49-60: Data will be obtained from practices' EHRs re. implementation (e.g., rate of screening, CM-related ICD-10 codes), final data analyses, prepare Final Report and papers

### **Procedures**

**Pre-implementation Phase** (5 months). Recruitment will begin and we will identify a physician "champion" and an office staff member to lead implementation in each practice. Practices will choose by month 4 SEEKonline or the Traditional paper and pencil approach. To ease introduction of the SEEK model, we will address logistical issues such as for which checkups parents will complete the SEEK PQ and documentation in the EHR. SEEK Parent Handouts will be customized with information on local resources and PCPs will complete the SEEK Primary Care Provider Questionnaire (PCPQ) prior to the SEEK training.

**Implementation Phase.** In month 5, practices in cohort 1 will be randomized to one of the two SEEK training strategies (MOC or IND), stratified by practice type (pediatric or family medicine). At the end of training in month 8, PCPs will evaluate it. After the training, PCPs will be asked to participate in 3 webinars

every 4 months to discuss implementation and clinical issues. By month 8, interested practices will have SEEKonline connected to their EHR, ensuring interoperability. In month 9, the SEEK intervention will begin in cohort 1. Practice leaders, PCPs, behavioral health professionals and office staff will be asked to complete the online SEEK Adoption Survey, regardless of full participation. Parents also will begin completing surveys. Purposive subsamples from each group will be selected for 30-minute phone qualitative interviews. The process for cohort 2 will begin in month 11 and the SEEK intervention will start in month 16. Procedures are detailed under Human Subjects for addressing concerns of possible child abuse or neglect.

**Sustainment Phase.** Participants will be assessed at 12, 21 and 33 months post baseline regarding their thinking, feeling, behavior and experiences (see Table 3) to help inform understanding of SEEK's implementation and sustainment. At months 41 and 48, the observation period will end for cohorts 1 and 2. Final surveys and phone interviews will assess participants' thoughts and plans about continued use of SEEK. Following the grant period, practices that wish to continue utilizing the implementation strategies will be guided through the process of establishing real-world, not-grant funded contracting.

**Final 12 months.** De-identified aggregate data will be obtained from practices' EHRs on all children (0-5) for the periods prior to and during SEEK implementation: rate of eligible visits where screening occurred, types of problems identified, types of actions taken, receipt of services, as well as CM-related diagnoses using ICD-10 codes. This will be facilitated by 4 of the 5 systems using EPIC as their EHR and having in-house IT. The data will be analyzed, the Final Report prepared, and presentations and papers will continue to be developed.

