**Table 4. Power Calculations**

Aim	Respondents/Source	Measure	N per group	Detectable Effects with 80% power
1a	PCPs	Changes in Comfort and Competence in addressing CM	137	Effect size  of 0.42
1a	Parents	Parent satisfaction	144	Effect size  of 0.41
1b	Staff	Staff Perceptions	24/72 	Effect size  of 0.82
2	Practices	Proportion adopting	59	Precision of +/- 15 pct points
3	EHR	Pre-post prevalence of CM-related diagnoses	98,000	5% vs. 4.5%  10% vs. 9.6%

Defined as the difference in means between groups divided by the standard deviation.

Conservatively assuming an imbalance between SEEKonline vs. Traditional of as much as 25% to 75%.

In our previous evaluations of SEEK, we observed rates of CM in the medical record ranging from 5% to 1%.

methods.

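### Procedures has practices choose SEEKonline or Traditional before randomisation, but the Aim 1a comparison of MOC with IND has no term for that choice

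*Combined protocol and SAP*

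**What the plan says.** - **Order of events, Procedures.** Under the pre-implementation phase, "Practices will choose by month 4 SEEKonline or the Traditional paper and pencil approach". The implementation phase follows: "In month 5, practices in cohort 1 will be randomized to one of the two SEEK training strategies (MOC or IND), stratified by practice type". No other stratification factor is named.
- **Order of events, Timeline.** The block for months 1-8 reads "Recruit practices and randomly assign to SEEK training strategies; complete training. Practices select SEEKonline or Traditional strategy", which lists selection after assignment and training. For cohort 2 the entry is only "Month 11-15: Repeat above process with cohort 2 of healthcare systems and practices"; no month is given for either the choice or the randomisation.
- **Self-selection.** The Design paragraph states: "Practices, however, will be able to select the facilitation strategy (SEEKonline or Traditional) as we are not able to require this of participants".
- **Factors handled by design.** The same paragraph states that "The design accounts for heterogeneity in geography, size of healthcare systems, type of primary care (pediatric and family medicine), and presence of integrated behavioral health". Delivery mode is not on that list, nor among the contextual factors that the Sample paragraph promises to consider in every analysis.
- **Aim 1a model.** The Data Analysis Plan shows one model, as an example for Competence. It has random effects for system, practice and PCP, and fixed terms for POST and POST by MOC. It contains no term for SEEKonline.
- **Aim 1b.** Practices choosing SEEKonline are compared with those choosing Traditional in a separate, non-randomised analysis.
- **Expected effect.** H2 in Specific Aims expects SEEKonline to increase delivery and penetration and to raise provider and parent satisfaction.

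**The concern.** If the choice is made by month 4 and randomisation is in month 5, delivery mode is a known practice characteristic at randomisation. The plan itself expects it to be prognostic for outcomes used in the randomised comparison: rates of screening, receipt of services and parent satisfaction appear under both Aim 1a and Aim 1b. With only 48 units to randomise, the arms can easily differ in their SEEKonline share by chance, and nothing in the allocation or the model corrects for that.

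At stake are the precision of the MOC versus IND estimate and how it will be read if the arms turn out unequal. A term prespecified now is uncontroversial. The same term added after a visible imbalance would look post hoc.

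The concern is confined to outcomes measured once SEEK is being delivered (from month 9 in cohort 1, month 16 in cohort 2). Training ends in month 8 for cohort 1, so use of SEEKonline can hardly affect scores taken straight after training.

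**Working it through.** **Inputs.** 48 practices, 13 pediatric and 35 family medicine (Sample). Two-sided 0.05 tests, a 1.5-fold variance inflation (Sample Size Considerations) and 80% power (Table 4). A SEEKonline share of 25% to 75% (Table 4, footnote 2). Assumed: 24 practices per arm, practices weighted equally, a 50% share as a middle case, and a SEEKonline effect of 0.2 to 0.82 SD, since the documents state no expected effect.

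**Step 1: reproduce Table 4.** Detectable effect = (1.96 + 0.84) × √(2 × 1.5 / n).

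| Row | Computed (normal / t) | Table 4 |
|---|---|---|
| PCPs, 137 per group | 0.415 / 0.417 | 0.42 |
| Parents, 144 per group | 0.404 / 0.406 | 0.41 |
| Staff, 24/72, effective 16/48: 2.80 × √(1/16 + 1/48) | 0.809 / 0.822 | 0.82 |

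The table reproduces. The standard error of the parent-satisfaction contrast is √(3/144) = 0.144 SD; for the PCP row it is √(3/137) = 0.148 SD.

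**Step 2: chance of imbalance.** With 12 SEEKonline practices among 48 and 24 allocated to MOC, the number in MOC is hypergeometric(48, 12, 24), and P(X ≤ 4) + P(X ≥ 8) = 0.318. Repeating this with stratification by practice type (13 and 35):

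| Practices choosing SEEKonline | SD of difference in share | P(arms differ by ≥ 4 practices) | P(≥ 6 practices) |
|---|---|---|---|
| 12 or 36 | 12.7 points | 32% | 10% |
| 24 | 14.7 points | 39% | 15% |

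Stratifying by practice type therefore does not reduce the risk.

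**Step 3: size of the shift.** Shift = difference in share × SEEKonline effect. An 8-4 split gives (8 − 4)/24 = 0.167.

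| Assumed SEEKonline effect | Shift, 8-4 split | Shift, 9-3 split (6/24 = 0.25) |
|---|---|---|
| 0.2 SD | 0.033 | 0.05 |
| 0.42 SD | 0.070 | 0.105 |
| 0.82 SD | 0.137 | 0.205 |

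For an 8-4 split the shift is 0.03 to 0.14 SD. Against the parent-satisfaction row (0.41), that is 0.033/0.41 = 8% to 0.137/0.41 = 33% of the detectable effect, and below one standard error (0.144). The SD scale suits satisfaction scores; screening and receipt of services, if modelled as binary, would shift on the log-odds scale.

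**Step 4: how far out 0.82 lies.** It is the minimum detectable difference for staff perceptions, not an expected effect. With 6 parents per practice, a 1.5 inflation implies an ICC of 0.5/(6 − 1) = 0.10. A 0.82 SD effect at a 25% share would alone add between-practice variance of 0.82² × 0.25 × 0.75 = 0.126, more than that allowance. It is an outer bound.

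**Step 5: what adjustment does to precision.** In the PCP row, m = 275/48 = 5.73 per practice and the implied ICC is 0.5/4.73 = 0.106. Removing variance e²s(1 − s) for effect e and share s gives a design effect of (1 − 0.106) + 5.73 × (0.106 − e²s(1 − s)). For e = 0.2 to 0.42 and s = 25% to 50% this is 1.25 to 1.46, and the detectable effect becomes 0.38 to 0.41 instead of 0.41. The gain is modest.

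**The case against.** **Randomisation already protects the contrast.** This stands. The unadjusted intention-to-treat estimate is unbiased in expectation, variation due to delivery mode enters the practice random effect, and Table 4 allows for clustering. A reader might infer that the MOC versus IND result is biased; the documents do not support that. What remains is conditional balance and precision.

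**The covariate may not be a baseline variable.** This also stands, and it conditions the fix. The Timeline order, and the missing months for cohort 2, leave open that practices choose after assignment. Training arm could then influence the choice: Table 1 gives MOC practices a QI project, and Table 2 lists ready aggregate data for QI as a SEEKonline feature. Adjusting for a choice made after assignment could remove part of the MOC effect. A reader might take adjustment to be beyond debate; it is safe only for a choice recorded before randomisation.

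**The model is only an example.** True, and it also omits practice type, the stratification factor. But no other Aim 1a model or covariate list names SEEKonline.

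**The size depends on the assumed effect.** Accepted. It is tempting to set a shift of about 0.13 SD against the 0.42 for PCP Comfort and Competence. That crosses outcomes: 0.82 belongs to staff perceptions, H1 ties comfort and competence to MOC, and no hypothesis predicts a SEEKonline effect on them.

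**Conclusion.** The point holds as a matter of conditional balance and precision. On the order given in Procedures, a practice-level variable that the plan expects to affect shared outcomes is known before randomisation and is left out of both the stratification and the Aim 1a model. With 12 of 48 practices choosing SEEKonline and 24 per arm, an 8-4 or worse split has a 32% chance. An 8-4 split moves the unadjusted contrast by about 0.03 to 0.14 SD across assumed effects of 0.2 to 0.82 SD, which is less than one standard error. Post-training scores are not affected.

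The conclusion rests on the month-4 choice preceding randomisation in both cohorts, which the documents state explicitly for cohort 1 only and which the Timeline puts in doubt.

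A reader might also infer that balancing or adjusting would cure uneven cells for H3 (MOC and SEEKonline together). It would not. With 12 choosers, perfect balance still gives cells of 6, 6, 18 and 18, because self-selection causes most of the unevenness, and a main effect with a POST interaction contains no MOC by SEEKonline term.

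**What to change.** 1. Reconcile the Timeline with Procedures, and state the month of choice and the month of randomisation for cohort 2.
2. Lock and record each practice's choice before randomisation in both cohorts.
3. Prespecify that recorded choice, not later use, as a fixed effect in the Aim 1a models for screening, receipt of services, satisfaction and later PCP follow-ups. Where the outcome has a baseline measure, add its interaction with POST.
4. Analyse practices by the recorded choice even if they later switch delivery mode.
5. If the choice cannot be fixed before randomisation, leave it out of the primary model and say why.

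The cost is one or two model terms and one dated field per practice, with no material loss of precision. Constrained randomisation within each cohort is optional. Full cross-stratification would be sparse, since 25% of 13 pediatric practices is about 3.
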